- I will ensure that any staff at my site(s) who are involved in the study conduct are adequately trained regarding this trial's operations, the protocol and their responsibilities. In the case of delegating any of my study responsibilities I will provide the sponsor with a delegation of investigators responsibilities log.
- I understand that the study may be terminated or enrollment may be suspended at any time by ViroMed, Inc. with or without cause, or by me or my institution if it becomes necessary to protect the best interest of the study patients.

Principal Investigator's Name (print)
mi d
Title
Address
Signature / Date

STUDY SYNOPSIS

PROTOCOL TITLE A Phase I/II, Open Label, Dose-Escalation Study to Assess the

Safety and Tolerability of VM202 in Patients with Painful Diabetic

Peripheral Neuropathy

STUDY PHASE I/II

INVESTIGATIONAL AGENT VM202

Dose Three doses will be tested: 4 mg, 8 mg and 16 mg VM202.

POPULATION Patients aged ≥ 18 years to ≤ 75 years diagnosed with painful

diabetic neuropathy in both lower extremities.

STUDY DESIGN A phase I/II, open label, dose-escalation, multicenter, 12-month

study designed to assess the safety and tolerability of unilateral intramuscular injection in the calf of VM202 in patients with painful diabetic peripheral neuropathy (DPN). The study will consist of three (3) cohorts with a total of 4 patients enrolled in

each cohort.

A Data Safety Monitoring Board (DSMB) will monitor patient safety throughout the study. After the first patient in a dose cohort completes the Day 30 follow-up evaluation and the other three patients enrolled in the same cohort complete at least the Day 14 follow-up (second dosing), an interim safety evaluation will be performed by the DSMB. If the DSMB recommends proceeding, the next dose cohort will be treated. This process will be repeated between the second and third dose cohort. All three dose cohorts will be followed for one year from the time of the first dose of study drug administration. If a dose limiting toxicity (DLT) is observed in one patient in any dose group, two additional patients will be added to the dose cohort in which the toxicity was observed. If no additional DLTs are observed in the 6 patients at

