observed. If no additional DLTs are observed in the 6 patients at this dose level, it will be considered the Maximum Tolerated Dose (MTD). If a DLT occurs in 2 patients at any dose level, then the preceding dose level will be considered the MTD. The study will be stopped in the event that 2 DLTs occur at any point in the study.

NUMBER OF PATIENTS 12 to a maximum of 14

INCLUSION CRITERIA

- 1. Age \geq 18 years to \leq 75 years;
- 2. Documented history of Type I or II diabetes with current treatment control (glycosylated hemoglobin A_{1c} of $\leq 10.0\%$);
- 3. Diagnosis of painful diabetic peripheral neuropathy in both lower extremities;
- 4. The physical examination component of the Michigan Neuropathy Screening Instrument Score (MNSI) is ≥ 3 at Screening;
- 5. Visual analog scale (VAS) score of ≥ 4 cm at Screening (0 cm = no pain 10 cm worst imaginable pain);
- 6. Stable treatment of diabetes for at least 3 months with no anticipated changes in medication regimen, and no new symptoms associated with diabetes;
- 7. Lower extremity pain for at least 6 months; and
- 8. If female of childbearing potential, negative pregnancy test at screening and using acceptable method of birth control during the study.

EXCLUSION CRITERIA

- 1. Peripheral neuropathy caused by condition other than diabetes;
- 2. Other pain more severe than neuropathic pain;
- 3. Progressive or degenerative neurological disorder;
- 4. Myopathy;
- 5. Inflammatory disorder of the blood vessels (inflammatory angiopathy, such as Buerger's disease);
- 6. Active infection:
- 7. Chronic inflammatory disease (e.g. Crohn's, Rheumatoid Arthritis)
- 8. Positive HIV or HTLV at Screening
- 9. Positive Hepatitis B or C as determined by Hepatitis B core antibody (HBcAB), antibody to Hepatitis B antigen (IgG and IgM; HbsAB), Hepatitis B surface antigen (HBsAg) and Hepatitis C antibodies (Anti-HCV), at Screening or known immunosuppression or on chronic treatment with immunosuppressive drugs, chemotherapy or radiation therapy;
- 10. Stroke or myocardial infarction within last 6 months;
- 11. Ophthalmologic conditions pertinent to proliferative retinopathy or conditions that preclude standard ophthalmologic examination:
 - Cataract surgery within 6 months of trial;
 - Vascular lesions of the anterior segment of the eye (infection or ulceration of the cornea, rubeotic glaucoma, etc);
 - Vascular lesions of the posterior segment of the eye or proliferative retinopathy, macular edema, s/p

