3.2. STUDY DESIGN

This is a phase I/II, open label, dose-escalation, multicenter, 12 month study. Patients with painful DPN will be screened for study eligibility after giving informed consent. Patients will be treated with 4 mg, 8 mg or 16 mg of VM202 by intramuscular injections in the right calf on Day 0 and again on Day 14. Study drug will only be administered unilaterally. If injection in the right leg is medically contraindicated, the left leg may be treated and noted on the appropriate case report form.

VM202 will be delivered in a solution of 0.5 mg VM202 / mL. Individual injections will be 0.5 mL. Patients in Cohort I will receive 2 mg of VM202 on Day 0 and Day 14 for a final dose of 4 mg; Cohort II will receive 4 mg of VM202 on Day 0 and Day 14 for a final dose of 8 mg; and Cohort III will receive 8 mg of VM202 on Day 0 and Day 14 for a final dose of 16 mg VM202. Table 2 lists the final dose and number of injections to be administered by study cohort. Patients will be followed for a period of 12 months.

Table 2. VM202 administration for each cohort

Сонокт	FINAL DOSE VM202	Number of Injections Day 0 Day 14		TOTAL VOLUME INJECTED
I	4 mg	8	8	8 mL
II	8 mg	16	16	16 mL
III	16 mg	32	32	32 mL

This is a dose escalation study. Cohorts of increasing dose will be enrolled sequentially. Dose escalation decisions (permission to treat at higher doses) will be made by the Data Safety Monitoring Board (DSMB) based on review of adverse events and on the occurrence of dose limiting toxicities (DLT) in each cohort. The decision to proceed to the next higher dose cohort will be made according to the following scheme.

After the first patient in a dose cohort completes the Day 30 follow-up evaluation and the other three patients enrolled in the same cohort complete at least the Day 14 follow-up (second dosing), an interim safety evaluation will be performed by the DSMB.

- If no DLT is observed at the current dose cohort, then the dose may be escalated as planned for the next cohort.
- If a DLT is observed in one patient in a dose group, then 2 additional patients will be treated at the same dose level. If no further DLTs are observed in the additional patients at Day 30, then that Dose will be considered the Maximum Tolerated Dose (MTD).
- If a DLT occurs in 2 patients, then the preceding dose level will be considered the MTD.

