If a DLT is observed in a patient in a dose cohort with complete enrollment, but after a dose escalation has occurred, further dose escalation may be delayed pending review of the data. If 2 patients in a dose cohort experience a DLT, then the study will be stopped.

A DLT is defined as any of the following SAEs:

- acute anaphylaxis (including erythema, hives, wheezing, stridor or respiratory distress) attributable to VM202 injection;
- temperature >102°F with negative blood cultures and in absence of viral syndrome within 24 hours of study drug administration; or
- evidence of active tissue necrosis of grade 3 or greater at the injection site within two weeks of study drug administration.

The DSMB will make a formal recommendation to proceed (or not proceed) to the next dose cohort between the first and second dose cohort, and again between the

second and third dose cohort (if applicable). The DSMB will monitor patient safety throughout the 12 month follow-up period.

[figure not shown]

Figure 3. Study flowchart

Screening/Baseline assessments should occur within the 60 days prior to Day 0 (day of injection). Baseline assessments include assessment of study eligibility, a complete medical history, vital signs, complete physical exam, photograph and measurement of ulcers (if any), cancer screening tests, viral screening, MNSI Score, VAS, 12 lead EKG, retinal fundoscopy, clinical chemistry, hematology, urinalysis, and pregnancy test (women of childbearing potential only), and documentation of any ulcers or gangrenous areas.

Patients will be treated with 8, 16 or 32 – 0.5 mL intramuscular injections in the right calf of VM202 on Day 0 and again on Day 14. Each injection will contain 0.25 mg VM202. The first cohort of patients will receive a total dose of 4 mg of study product in 8 mL of solution (eight injections on Day 0, and eight injections on Day 14). The second cohort of patients will receive a total dose of 8 mg of study product in 16 mL of solution (sixteen injections on Day 0, and sixteen injections on Day 14). The third cohort of patients will receive a total dose of 16 mg of study product in 32 mL of solution (thirty-two injections on Day 0, and thirty-two injections on Day 14).

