3.3. PATIENT POPULATION

Up to 14 evaluable patients with DPN meeting the following study entry criteria will be enrolled.

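### The DLT definition covers three acute reactions only, so other SAEs probably or definitely related to VM202 or the injections do not count toward the expansion, MTD or two-patient stop rules; a cheap addition would close this

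*Combined protocol and SAP*

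**What the plan says.** Section 3.2 introduces the definition with "A DLT is defined as any of the following SAEs". Three items follow, and there is no general item for other related SAEs:

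- acute anaphylaxis attributable to VM202;
- temperature above 102°F within 24 hours of dosing, with negative cultures and no viral syndrome;
- active tissue necrosis of grade 3 or greater at the injection site within two weeks of dosing.

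The rules that use the definition are these:

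- **Expansion.** In the synopsis, if a DLT "is observed in one patient in any dose group, two additional patients will be added to the dose cohort". Section 3.2 has the same rule.
- **MTD.** If the two added patients have no DLT by Day 30, that dose is the MTD. If two patients have a DLT, the preceding dose is the MTD.
- **Stop.** Section 3.2: "If 2 patients in a dose cohort experience a DLT, then the study will be stopped". Synopsis: "The study will be stopped in the event that 2 DLTs occur at any point in the study".
- **DLT found after escalation.** Section 3.2: "further dose escalation may be delayed pending review of the data".

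DSMB decisions on escalation are "based on review of adverse events and on the occurrence of dose limiting toxicities (DLT) in each cohort". With no DLT, the dose may be escalated but need not be. Formal DSMB recommendations fall between Cohorts I and II and between Cohorts II and III, and the DSMB monitors safety for 12 months. The sponsor may end the study for any safety reason (3.5.3). SAEs go to the sponsor within 48 hours (5.4.1).

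**The concern.** Section 6 gives the primary goal as finding a maximum tolerated dose that ensures patient safety, yet the rule that assigns this label sees only three acute reactions. The SAE definition in 5.1 is far wider and includes death, life-threatening events and permanent impairment.

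Two examples fall outside the list on its wording: a serious injection-site ulceration of grade 3 without necrosis (Table 3 grades ulceration in its own row), and necrosis that begins more than two weeks after a dose.

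Two patients in one cohort could have life-threatening SAEs judged definitely related, and no prespecified expansion, pause or stop would follow. The response would rest on judgement with no stated threshold. At 16 mg there is also no escalation left to withhold.

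**Working it through.** **1. Planned size.** 3 cohorts × 4 = 12, and one expansion gives 12 + 2 = 14. This reproduces the stated 12 to 14, and the point does not dispute it.

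**2. What an off-list related SAE does under the present rules.**

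| Rule | What it counts | Effect of an off-list related SAE |
|---|---|---|
| Add two patients | DLT in one patient | none |
| This dose is the MTD | no further DLT in the added patients | none |
| Preceding dose is the MTD | DLT in two patients | none |
| Mandatory stop | two patients (3.2) or two DLTs (synopsis) | none |
| DSMB escalation decision | adverse events and DLTs | can withhold escalation, no threshold |
| Sponsor termination | any safety reason | can stop, no threshold |

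**3. Size, for illustration.** Let *s* be the chance per patient of an event meeting the proposed fourth item. The documents give no value, so I assume 2%, 5% and 10%, equal at every dose and independent between patients, with no listed DLTs. The chance of at least one such event in a cohort of 4 is 1 − (1 − *s*)⁴ = 8%, 19% and 34%. The present rules count none of them.

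**4. Where the MTD label is affected.** The label goes to a dose with one listed DLT in 6 patients. The chance that at least one of the other 5 has an off-list event is 1 − (1 − *s*)⁵ = 10%, 23% and 41%. Once counted, that would be the second affected patient. These figures are conditional on a listed DLT having occurred.

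**5. Effect of adding the item.** Let *q* = (1 − *s*)⁴, *p*₁ = 4*s*(1 − *s*)³ and *p*₂ = 1 − *q* − *p*₁. At the DSMB review the first patient has reached Day 30, but the other three may have reached only Day 14. Let *f* be the share of those three patients' events known by then. A single affected patient is then known with probability *k* = 0.25 + 0.75*f*. Cohort III uses *f* = 1, because no escalation follows.

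- Stop in one cohort: *T* = *p*₂ + *p*₁*k*[1 − (1 − *s*)²]; *T*₁ is *T* at *f* = 1.
- Go on to the next cohort: *c* = *q* + *p*₁(1 − *k*).
- Study stopped (3.2 wording): *T*(1 + *c*) + *c*²*T*₁.
- Expanded once, that dose labelled MTD: (1 − *s*)²*p*₁[*k*(1 + *c*) + *c*²].
- Neither: *c*²*q*.

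Example, *s* = 5% and *f* = 1: *q* = 0.8145, *p*₁ = 0.1715, *p*₂ = 0.0140.

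- *T* = 0.0140 + 0.1715 × 0.0975 = 0.0307.
- Stopped: 0.0307 × 1.8145 + 0.6634 × 0.0307 = 0.076.
- Expanded: 0.9025 × 0.1715 × 2.478 = 0.383.
- Neither: 0.8145³ = 0.540, so stopped or capped = 0.460.

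At *f* = 0, *c* = 0.8145 + 0.1715 × 0.75 = 0.943. Neither = 0.943² × 0.8145 = 0.724, so stopped or capped = 0.276.

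Results, with ranges from *f* = 0 to *f* = 1:

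| *s* | Stopped | Expanded once, labelled MTD | Stopped or capped |
|---|---|---|---|
| 2% | 1.1–1.5% | 11–20% | 12–22% |
| 5% | 6–8% | 21–38% | 28–46% |
| 10% | 21–22% | 29–49% | 50–72% |

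The last column includes outcomes reached in Cohort III, where 16 mg has already been given. If the synopsis stop wording governs, stopping rises to at most 2.3%, 12% and 33%.

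**6. Enrolment.** An expansion that ends escalation gives 4 + 2 = 6, 4 + 4 + 2 = 10 or 4 + 4 + 4 + 2 = 14 patients for Cohort I, II or III. If a DLT found late in an earlier cohort also added two, as the synopsis wording allows, the total could reach 14 + 2 = 16. Section 3.3 says "Up to 14 evaluable patients with DPN meeting the following study entry criteria will be enrolled".

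**The case against.** The strongest reply is that escalation already has a gate for off-list events. DSMB permission rests on adverse events as well as DLTs, a cohort without DLTs only may be followed by a higher dose, and a formal recommendation is required. With four patients per cohort, leaving unlisted events to judgement is a defensible choice. This stands, and it rules out one tempting inference: that a related death outside the list would be ignored. It would be reported, reviewed, analysed, and could end escalation or the study.

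A second tempting inference is that the MTD label is generally unsafe. The documents do not support that either. An MTD is named only once a listed DLT has occurred, so the label goes wrong only when a listed DLT and off-list related SAEs occur together. Sections 3.1 and 6.2 also state the aim more broadly, as safety and tolerability.

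It is also fair to say that a broader definition costs something: it could often cap or end a small study. Counting possibly related events would make this worse, since SAEs from coexisting disease are to be expected in diabetic patients. That is a reason to limit the counted item to probable or definite relation and to Day 30, and to handle graver events that are only possibly related, or later, by a pause.

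None of this supplies a count, threshold or dosing pause for off-list related SAEs, nor anything specific at 16 mg.

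**Conclusion.** The point holds as a cheap safety improvement, not as a fatal flaw. The closed list and the DLT-only rules are plain in the text. The gap lies in the automatic rules and the MTD label; DSMB and sponsor discretion cover the rest without a stated trigger.

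The probabilities show how the rules behave at assumed rates. They are not estimates of VM202's risk, and they rest on equal rates across doses, independent patients and no listed DLTs. I take no position on whether a product-specific rationale for the three items exists.

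**What to change.** 1. Add a fourth DLT item in Section 3.2: *any other SAE assessed as probably or definitely related to VM202 or the injection procedure with onset through Day 30*, with clinical wording agreed with the DSMB. Day 30 is the horizon already used for the added patients.
2. State that any fatal or life-threatening SAE at least possibly related to VM202 or the procedure, at any time in follow-up, pauses dosing until DSMB review.
3. State that any DLT, listed or new, found after escalation counts toward the two-patient stop and prompts a pause and DSMB review, but adds no patients. This must cover listed DLTs too: necrosis after the Day 14 dose can arise up to about Day 28, after the review. Enrolment then stays within 14, apart from the replacements allowed in Section 3.5.2. Make the matching edits in the synopsis, including its stop rule.
4. State that if two patients in Cohort I have a DLT, no MTD is identified, because there is no preceding dose.

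The cost is a few sentences in Section 3.2 and the synopsis. No new data are needed, since Sections 5.2 and 5.2.1 already record relatedness to drug and procedure. The real price is the higher chance of expansion, capping or stopping tabulated above, which the sponsor and DSMB should accept knowingly.

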3.5.3. PREMATURE STUDY TERMINATION

The Sponsor reserves the right to discontinue the study for any safety, ethical or administrative reason at any time.

INVESTIGATIONAL DRUG PRODUCT AND ACCOUNTABILITY

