4.2.11. INJECTION SITE REACTION ASSESSMENT

Local injection sites reactions will be assessed on Day 0 post injection, Day 14, Day 21, Day 30 and Day 60 using the grading defined by the National Cancer Institute's Common Terminology for Adverse Events v3.0. The grading categories are as follows and will be recorded on the CRF as described in

Table 3. Injection Reaction Assessment

Table 3.

ADVERSE EVENT	GRADE 1	GRADE 2	GRADE 3	GRADE 4	GRADE 5
Injection site reaction	Pain, itching, erythema	Pain or swelling, with inflammation or phlebitis	Ulceration or necrosis that is severe; operative intervention indicated		
Ulceration		Superficial ulceration < 2 cm size; local wound care; medical intervention indicated	Ulceration ≥2 cm size; operative debridement, primary closure or other invasive intervention indicated (e.g. hyperbaric oxygen)	Life- threatening consequences; major invasive intervention indicated (e.g., complete resection, tissue reconstruction, flap, or grafting	Death
Allergic reaction / hypersensitivity	Transient flushing or rash; drug fever < 38°C (<100.4°F)	Rash; flushing ; urticaria; dyspnea; drug fever ≥38°C (≥100.4°F)	Symptomatic bronchospasm, with or without urticaria; parenteral medications(s) indicated; allergy- related edema/ angioedema; hypotension	Anaphylaxis	Death

5. **EVALUATION OF ADVERSE EVENTS**

5.1. **DEFINITIONS**

An Adverse Event (AE) is the development of an untoward medical occurrence or the deterioration of a pre-existing medical condition following or during exposure to an investigational product, whether or not considered causally related to the product.

An untoward medical condition can be symptoms (e.g., nausea, chest pain), signs (e.g., tachycardia, enlarged liver) or clinically significant abnormal results of an investigation (e.g., laboratory findings, electrocardiogram).

A serious adverse event (SAE) is any untoward medical occurrence which:

- Results in death;
- Is life-threatening;
- Requires inpatient hospitalization or prolongation of hospitalization which is not specifically required by the protocol or is elective;
- Results in permanent impairment of a body function or permanent damage to a body structure; or
- Requires medical or surgical intervention to preclude permanent impairment of a body function or permanent damage to a body structure.

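### A serious grade 3 or higher injection-site ulcer with no evidence of necrosis is not a DLT, so the written expansion, MTD and stopping rules cannot act on it

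*Combined protocol and SAP*

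**What the plan says.** Section 3.2 introduces the list with "A DLT is defined as any of the following SAEs". Three items follow and there is no catch-all. Two are systemic: anaphylaxis attributable to the injection, and high fever within 24 hours of dosing. The third is "evidence of active tissue necrosis of grade 3 or greater at the injection site within two weeks of study drug administration".

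The count of these events drives the written rules:

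- No DLT: "If no DLT is observed at the current dose cohort, then the dose may be escalated as planned for the next cohort".
- One DLT: 2 patients are added at that dose. If they are clean at Day 30, that dose is the MTD.
- Two DLTs: the preceding dose is the MTD and "If 2 patients in a dose cohort experience a DLT, then the study will be stopped". The synopsis adds that 2 DLTs at any point stop the study.

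The DSMB decides on escalation "based on review of adverse events and on the occurrence of dose limiting toxicities (DLT) in each cohort". Section 3.5.3 adds: "The Sponsor reserves the right to discontinue the study for any safety, ethical or administrative reason at any time".

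On local reactions, section 4.2.11 says: "Local injection sites reactions will be assessed on Day 0 post injection, Day 14, Day 21, Day 30 and Day 60". In Table 3, the injection site reaction row gives severe ulceration and severe necrosis as alternatives at grade 3. A separate ulceration row runs from grade 2 to grade 5. Its grade 3 is an ulcer of at least 2 cm for which an invasive procedure is indicated, grade 4 is life-threatening, and grade 5 is death. No grade in that row requires necrosis.

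**The concern.** The protocol ranks severe ulceration with severe necrosis, then makes only necrosis dose-limiting and gives no reason. Section 6 states that the primary goal is to determine the MTD, and the MTD is defined entirely through DLTs. If a serious ulcer cannot be a DLT, a dose that produces one can pass through the written scheme with a clean count.

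Local injury is a natural risk to bound in this trial. Cohort III patients receive 32 injections into one calf on each of two days, and section 1.1.1 notes that the disease predisposes to foot ulceration. Against that, the only toxicity that section 1.5 reports from the animal studies was mild, transient injection-site irritation.

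**Working it through.** This is a question of rule logic, so the check sets the texts side by side.

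**Step 1. The plan's own sample size.** 3 cohorts × 4 patients = 12. One expansion of 2 gives 12 + 2 = 14. Both agree with the synopsis (12 to a maximum of 14).

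**Step 2. Is the event on the list?** It is a serious ulcer at the injection site, grade 3 or higher, within two weeks of dosing, with no evidence of necrosis. It is not anaphylaxis or fever, and it does not meet the third item, which asks for necrosis.

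**Step 3. Does the SAE requirement explain the omission?** No. Under section 5.1, death and life-threatening events are SAEs, which covers ulceration grades 5 and 4. A grade 3 ulcer is an SAE if surgery is needed to prevent permanent damage, or if it leads to a non-elective hospital admission that the protocol does not require. Such ulcers can pass the SAE requirement and still not be DLTs.

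**Step 4. What the written rules do.** For events in one cohort of 4, all seen before the DSMB review:

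| Patients with the event | DLT count as written | Action as written | Count if the event were a DLT | Action if the event were a DLT |
|---|---|---|---|---|
| 1 | 0 | dose may be escalated, subject to the DSMB | 1 | 2 patients added; that dose is the MTD if they are clean |
| 2 | 0 | same | 2 | study stops; preceding dose is the MTD (Cohort I has none) |
| 4 | 0 | same | 4 | study stops |

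The synopsis rule of 2 DLTs at any point is equally silent as written, because these events never enter the count.

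**Step 5. When would a counted event act automatically?** The DSMB review needs the first patient at Day 30 and the other three only at Day 14, the day of second dosing. For up to 3 of 4 patients, the two weeks after the second dose can therefore fall after the review. For a single DLT that appears after escalation, section 3.2 says only that further escalation may be delayed while the data are reviewed. The stopping rules for 2 DLTs still apply.

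**Step 6. Sample size if the event counted.** An expansion before escalation gives a total of 4 + 2 = 6 in Cohort I, 4 + 6 = 10 in Cohort II, or 4 + 4 + 6 = 14 in Cohort III. All are within the ceiling of 14.

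**Step 7. Frequency.** The documents give no rate for this event and nothing from which to derive one. Any probability would only restate an assumed rate, so none is offered.

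**The case against.** The strongest reply is that the event is already covered. Adverse events are a second written basis for the DSMB's decision, escalation with no DLT is permitted but not required, and the DSMB must formally recommend whether to proceed. SAEs reach the sponsor within 48 hours (section 5.4.1), and the sponsor may stop for any safety reason. This stands. A reader might infer that patients would be escalated past serious ulcers unprotected, or that the DSMB would be bound to proceed. The documents support neither. But none of these provisions sets a threshold for ulceration, and the written scheme assigns an MTD only through DLTs.

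A second reply is that the class is nearly empty. The item asks only for evidence of necrosis, and many ulcers deep enough for debridement or grafting will show some. This also stands, and it limits the importance of the point. It does not settle how a multicenter trial would classify an ulcer without necrosis. One could argue that investigators would treat the two as equivalent, but the DLT text does not say so and Table 3 separates them.

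A third reply is that counting the event would not make the response automatic in every case. That is right for a single late event, as step 5 shows.

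A reader might also infer that the words after grade 3 in the DLT item are empty, because the one Table 3 row naming necrosis stops at grade 3. The documents do not settle this: the item cites no table, and a necrotic ulcer might be graded in the ulceration row. The point does not depend on it.

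**Conclusion.** The concern holds in a limited form. As written, a serious grade 3 or higher injection-site ulcer with no evidence of necrosis contributes 0 to the DLT count, however many patients have it, and cannot trigger expansion, set the MTD or stop the study by rule. Patients keep the protection of DSMB review and sponsor discretion. What is missing is consistency between the DLT list and the protocol's own grading of local reactions, in a trial whose primary goal is the MTD. The importance is minor to moderate.

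This rests on reading the DLT list as closed and taking the word necrosis at its plain meaning. It does not rest on any event rate. It would be going too far to say that the MTD is likely to be wrong, or to attach a probability to that.

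**What to change.** Replace the third DLT item in section 3.2 with wording to this effect:

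*Ulceration or active tissue necrosis at the injection site, new or worsened since the first study injection, of grade 3 or greater in either the Injection site reaction row or the Ulceration row of Table 3 (the higher grade counts), within two weeks of study drug administration.*

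Keep the SAE requirement and the DSMB review as they are. Naming Table 3 also settles which grading applies. The new-or-worsened condition is needed because section 4.2.7 allows for ulcers present before treatment without confining them to the foot, while Appendix 4 spreads the injections over the whole calf.

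The cost is one bullet. Table 3 grades already go on the CRF at the visits in section 4.2.11, so no procedure or field is added. The downside is real. One such event before the DSMB review adds 2 patients and, if they are clean, ends escalation at that dose. A second in the same cohort stops the study, and under the synopsis so does a second anywhere in the trial. The plan already accepts these consequences for necrosis of the same grade.
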